#### **5.4.3.5. Urinalysis Tests with Categorical Results**

Results of urinalysis with qualitative results will be tabulated by time point. No toxicity grading or non-graded abnormalities will be derived.

#### **5.4.3.6. Treatment Emergent Principle**

##### **Toxicity Grades**

A post-baseline toxicity grade 1, 2, 3 or 4 is defined as treatment-emergent when higher than the toxicity grade of the baseline result. If the baseline result is missing, a post-baseline toxicity grade 1, 2, 3 or 4 will always be considered as treatment-emergent.

For prothrombin time parameter a post-baseline value meeting the defined abnormality criteria is regarded as treatment-emergent if the post-baseline criteria meet a higher degree of abnormality than the baseline value (e.g. post-baseline value meeting >1.5-2.5 x ULN category while baseline meeting >ULN-1.5 x ULN category) or the baseline value is missing or does not meet any abnormality criteria. For glucose [fasting], high density lipoprotein and low density lipoprotein a post-baseline abnormal category will be regarded as treatment emergent, if the baseline value is missing or does not meet the defined abnormality criteria.

##### **Non-graded Abnormalities**

A post-baseline non-graded abnormality class L or H is defined as treatment-emergent when it differs from the abnormality class of the baseline result. If the baseline result is missing, a post-baseline abnormality L or H will always be considered as treatment-emergent.

---

#### **5.4.3.7. Worst-Case**

##### **Toxicity Grading**

The worst-case post-baseline toxicity grade 0, 1, 2, 3 or 4 will be determined per subject, per parameter (and sense, if below and above) during the on-treatment analysis period, using all non-missing post-baseline records within that period (including unscheduled and follow-up visits).

The worst-case toxicity grade is the highest toxicity grade scored for the parameter (in each sense, if below and above).

##### **Non-graded Abnormalities**

The following worst-case post-baseline abnormalities L, N or H will be determined per subject, per parameter and for the on-treatment analysis period, using all non-missing post-baseline records within that period (including unscheduled and follow-up visits):

- L = low: at least one post-baseline result is classified as L.
- N = normal: all post-baseline results are classified as N.
- H = high: at least one post-baseline result is classified as H.

If, for a subject, both L and H are reported, the subject will be counted twice in the table: once with a worst-case L and once with a worst-case H.

#### 5.4.3.8. Elevated Liver Function Test

To assess the potential of the IMP to cause severe liver damage, possible Hy's Law cases will be identified. Count and percentage of subjects who have at least one assessment meeting the criteria defined in [Table 5](#) will be summarized in the on-treatment analysis period.

**Table 5: Hepatotoxicity**

Parameter	Thresholds
AST / ALT combination	AST > 1.5- <3 x ULN AST ≥ 3- <5 x ULN AST ≥ 5- <8 x ULN AST ≥ 8 x ULN  ALT > 1.5- <3x ULN ALT ≥ 3- <5 x ULN ALT ≥ 5- <8 x ULN ALT ≥ 8 x ULN  ALT and/or AST > 1.5 -<3 x ULN AST and /or ALT ≥ 3- <5 x ULN AST and /or ALT ≥ 5- <8 x ULN AST and /or ALT ≥ 8 x ULN
AST / ALT / bilirubin combination	Bilirubin ≥ 1.5 x ULN AND AST or ALT ≥ 3 x ULN  Bilirubin ≥ 2 x ULN AND AST or ALT ≥ 3 x ULN

Hepatotoxicity values will also be listed including the timing of occurrence.

#### 5.4.3.9. Presentation of Results

No formal inferential statistics (p-values) will be provided.

Continuous parameters will be summarized by means of descriptive statistics (including 95% CI of the mean change from t-test) by parameter, treatment group and analysis visit. Actual values and changes from baseline will be tabulated separately.

Figures of the mean ( $\pm$  SE) actual values over time and of the mean ( $\pm$  SE) change from baseline will be prepared for all parameters.

All laboratory abnormalities after the first dose of study medication up to 30 days after the last dose, if the subject did not enroll in the OLE study, or the earliest between the last IMP intake + 30 days during the double-blind study and the first dose of IMP in the OLE study (excluded), if the subject continues in OLE, will be included.

Abnormalities of the actual values will be presented as shift tables of the worst-case abnormality versus the baseline abnormality/toxicity grade. The table will be created per parameter and treatment group for the on-treatment analysis period. The results of non-graded abnormalities and toxicities grades will be shown separately.

---

A frequency table of the number (percentage) of subjects with treatment-emergent worst-case abnormalities per parameter and treatment group for the on-treatment analysis period will be presented. The results of non-graded abnormalities and toxicities grades will be shown separately.

Urinalysis tests for which no normal range is available will be tabulated separately as categorical data.

Clinical laboratory values will also be listed including normal ranges and indicating if value is out of range. Separate listings will also be created to include all laboratory values of a subject who has had at least one value meeting CTCAE grading 3 or higher category.

#### **5.4.4. Electrocardiogram**

##### **5.4.4.1. Available Data**

All subjects will have a standard 12-lead electrocardiogram (ECG) performed at the time points specified in the Schedule of Activities (see [Appendix 1](#)). The following ECG parameters will be analyzed: heart rate (bpm), PR interval, QRS interval, uncorrected QT interval (ms), morphology, QT interval corrected for the heart rate using Fridericia's formula (QTcF) (ms).

##### **5.4.4.2. Derivation Rules**

###### **Derived Parameters**

The ECG parameters will be provided in the clinical database, no imputation will be done.

###### **Handling of ECGs Measured in Triplicate**

If ECG is collected in triplicates (or duplicates), the following approach will be taken.

The mean of the triplicate (or duplicate) ECG values will be calculated for each individual ECG parameter, without rounding the result. These calculated means will constitute the analysis values; any derivation (e.g. change from baseline, assignment of abnormalities) and statistic will be based on the mean value of the triplicates (or duplicates).

When a single ECG is performed, the actual results of the single ECG will be summarized.

The values of the individual triplicate (or duplicate) assessments will be listed, i.e. will not be summarized or graphically presented.

**5.4.4.3. Abnormalities**

The actual analysis values and changes from baseline of the QT and QTcF parameters will be categorized into the abnormality classes as defined in [ICH E14](#):

**Table 6: Abnormalities on ECG Parameters**

Parameter	Abnormality	Limits
Abnormalities on actual values		
QT and QTcF (ms)	QT* ≤ 450 450 < QT* ≤ 480 480 < QT* ≤ 500 QT* > 500	≤ 450 450 < value ≤ 480 480 < value ≤ 500 > 500
Abnormalities on change from Baseline		
QT and QTcF (ms)	QT* change ≤ 30 30 < QT* change ≤ 60 QT* change > 60	≤ 30 30 < value ≤ 60 > 60

\* Indicate which QT(c) parameter is analyzed in the label

**Worst-Case Abnormality**

The worst-case post-baseline categorized actual analysis value and the worst-case categorized change from baseline for QT and QTcF will be determined per subject, per parameter, using all non-missing post-baseline records (including unscheduled and follow-up visits) for the on-treatment analysis period.

The worst-case categorized actual analysis value is the category corresponding to the highest post-baseline actual value.

The worst-case change from baseline is the category corresponding to the largest increase (positive change) from baseline.

For the overall interpretation the worst-case post-baseline will be determined per subject, per parameter, and for on-treatment analysis period, using all non-missing post-baseline records (including unscheduled and follow-up visits) as follow:

- Normal: if all the post-baseline results are normal
- Abnormal: if at least one post-baseline result is abnormal.

**Treatment Emergent Abnormalities**

Actual value: An abnormal post-baseline abnormality is defined as treatment-emergent when the abnormality is worse compared to the abnormality at baseline. If the baseline result is missing, a post-baseline result outside of the normal range will always be considered as treatment-emergent.

An abnormal category for change from baseline is always treatment-emergent.

#### 5.4.4.4. Presentation of Results

No formal inferential statistics (p-values) will be presented.

Continuous parameters will be summarized by means of descriptive statistics (including 95% CI of the mean change from t-test) by parameter, treatment group and analysis visit. Actual values and changes from baseline will be tabulated separately.

All ECG abnormalities after the first dose of study medication up to 30 days after the last dose, if the subject did not enroll in the OLE study, or the earliest between the last IMP intake + 30 days during the double-blind study and the first dose of IMP in the OLE study (excluded), if the subject continues in OLE, will be included.

Abnormalities of the actual values will be presented as shift tables of the worst-case abnormality versus the baseline abnormality. The table will be created per parameter, treatment group for the on-treatment analysis period.

A frequency table of the number (percentage) of subjects with treatment-emergent worst-case abnormalities per parameter, treatment group for the on-treatment analysis period will be presented. Overall interpretation as assessed by the investigator will also be summarized.

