### **QT Interval Prolongation**

The potential effect of GLPG1690 on QT interval prolongation is not fully known. Consequently, subjects with long QT syndrome or QTcF >450 ms during screening will be excluded. The chronic use or initiation of medication known to prolong the QT interval needs to be evaluated on a case-by-case basis. Periodic ECG recording and monitoring with central reading will be implemented for the duration of the study. A list intended as guidance for the investigator is provided in [Appendix 5](#).

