#### Secondary Objective

- To evaluate the safety and tolerability of GLPG1690 compared to placebo over 24 weeks in the treatment of subjects with systemic sclerosis

---

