## 5.4. SAFETY ANALYSES

Safety analyses will be performed on the Safety Set.

No formal testing will be performed to compare the treatment groups.

Tabulations will be shown by treatment group.

---

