### 5.4.5.5. Presentation of Results

No formal inferential statistics (p-values) will be derived.

Continuous parameters will be summarized by means of descriptive statistics (including 95% CI of the mean change from a t-test) for all vital sign parameters and analysis visits, by treatment group and overall for subjects in the applicable Safety Set. Actual values and changes from baseline will be tabulated separately.

All abnormalities after the first dose of study medication up to 30 days after the last dose, if the subject did not enroll in the OLE study, or the earliest between the last IMP intake + 30 days during the double-blind study and the first dose of IMP in the OLE study (excluded), if the subject continues in OLE, will be included.

Abnormalities of the actual values will be presented as shift tables of the worst-case abnormality versus the baseline abnormality. The table will be created per parameter and treatment group for the on-treatment analysis period.

A frequency table of the number (percentage) of subjects with treatment-emergent worst-case abnormalities per parameter, treatment group for the on-treatment analysis period will be presented.

Mean ( $\pm$  SE) plots over time for both treatment groups, with heart rate, respiratory rate, and blood pressure by position on a new page, will be displayed.

- | [REDACTED]
- | [REDACTED]
- | [REDACTED]
- | [REDACTED]
- | [REDACTED]
- | [REDACTED]
- | [REDACTED]
- | [REDACTED]
- | [REDACTED]
- | [REDACTED]
- | [REDACTED]

[REDACTED]

[REDACTED]

- | [REDACTED]

[REDACTED]

[REDACTED]

[REDACTED]

[REDACTED]

[REDACTED]

[REDACTED]

[REDACTED]

[REDACTED]

[REDACTED]

[REDACTED]

[REDACTED]

[REDACTED]

[REDACTED]

[REDACTED]

[REDACTED]

[REDACTED]

[REDACTED]

[REDACTED]

[REDACTED]

[REDACTED]

[REDACTED]

[REDACTED]

[REDACTED]

[REDACTED]

[REDACTED]

---

[REDACTED]

[REDACTED]

## APPENDIX 1

EVENT	SCREENING	TREATMENT PERIOD									FOLLOW-UP i	
		1	2	3	4	5	6	7	8	9	ED a	FU1
Study Day (D) or Week (W) b ± days (d)	D-28 to D-1	D1	W2 ±2d	W4 ±2d	W8 ±4d	W12 c ±4d	W16 ±4d	W20 c ±4d	W24 i ±4d		W28 ±7d	W36 ±7d
Informed consent	✓											
Inclusion/exclusion criteria	✓	✓										
Demographics	✓											
Medical history/concurrent illnesses	✓											
FSH test	✓											
Randomization		✓										
Phone call						✓		✓				
Pregnancy test d	✓	✓		✓	✓	✓	✓	✓	✓	✓	✓	
Physical examination	✓	✓	✓	✓	✓		✓		✓	✓	✓	

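### The SAP's intervals for ECG, laboratory and vital-sign changes are within-arm only; a descriptive interval for the difference from placebo should be added

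*SAP*

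**What the plan says.** SAP 5.4.4.4 summarises continuous ECG parameters by "descriptive statistics (including 95% CI of the mean change from t-test) by parameter, treatment group and analysis visit". SAP 5.4.3.9 uses the same wording for laboratory parameters. SAP 5.4.5.5 plans "descriptive statistics (including 95% CI of the mean change from a t-test) for all vital sign parameters and analysis visits", given by treatment group and also for all subjects together.

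The SAP frames all this as description. Section 5.4 states "No formal testing will be performed to compare the treatment groups" and "Tabulations will be shown by treatment group". Section 5.4.4.4 adds "No formal inferential statistics (p-values) will be presented", and 5.4.3.9 and 5.4.5.5 say the same in substance.

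The secondary objective (SAP 2.1) is comparative: "To evaluate the safety and tolerability of GLPG1690 compared to placebo over 24 weeks in the treatment of subjects with systemic sclerosis". Protocol 4.4 says of one measure concerned: "The potential effect of GLPG1690 on QT interval prolongation is not fully known".

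For mRSS, SAP 5.3.2.3 does plan a between-arm quantity: the difference in LS means with a 95% CI at each time point. The readable safety sections contain no counterpart. Parts of the SAP are redacted, so this holds for the readable text only.

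**The concern.** A t interval for a mean change, produced by treatment group, is naturally read as a one-sample interval. Its reference value is zero change from baseline in that arm. The objective's reference value is zero difference in change between GLPG1690 and placebo. The two questions coincide only if placebo subjects do not change on average, and background treatment and disease course over 24 weeks make that uncertain. The overall interval for vital signs pools the arms and so does not compare them either.

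At stake is how the tables are read. With unequal arms the two printed intervals differ in width, so the same true change can leave the GLPG1690 interval clear of zero and the placebo interval across it. A reader could take that contrast for a drug effect. In the other direction, a placebo change that a drug effect offsets leaves the GLPG1690 interval covering zero. In neither case does a table bound the mean change relative to placebo, which is the quantity of interest for QTcF.

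**Working it through.** **Inputs.** Planned arms of 20 and 10, a 10% dropout (18 and 9 evaluable), an SD of 5 for mRSS change and a true difference of 4.7 all come from SAP 2.6. The documents give no SD and no expected placebo change for any safety parameter. Safety results are therefore in SD units, and the size of a shared change is an assumption. Changes are taken as normal with equal SD in both arms.

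**The plan's own design figure.** SAP 2.6 states a 63% chance of observing an mRSS effect above 4 points.
- SE at 18 vs 9 = 5 × √(1/18 + 1/9) = 2.041
- Φ((4.7 − 4)/2.041) = Φ(0.343) = 63.4%

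This reproduces the figure (64.1% at 20 vs 10). The documents state no precision for the safety intervals.

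**Half-widths of the 95% intervals, in SD units.** Within an arm: t(0.975, n−1)/√n. Between arms: t(0.975, n₁+n₂−2) × √(1/n₁ + 1/n₂).

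| | 20 vs 10 | 18 vs 9 |
|---|---|---|
| GLPG1690, within arm | 2.093/√20 = 0.47 | 2.110/√18 = 0.50 |
| Placebo, within arm | 2.262/√10 = 0.72 | 2.306/√9 = 0.77 |
| Difference | 2.048 × 0.387 = 0.79 | 2.060 × 0.408 = 0.84 |

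The placebo interval is 0.72/0.47 ≈ 0.77/0.50 ≈ 1.5 times as wide as the GLPG1690 interval.

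**No drug effect, same true change of d SD in both arms.** The chance that a within-arm interval excludes zero comes from the noncentral t with noncentrality d√n. The arms are independent, so the chance that only the GLPG1690 interval excludes zero is P(GLPG1690) × (1 − P(placebo)).

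| Arms | d | GLPG1690 excludes 0 | Placebo excludes 0 | Only GLPG1690 | Both |
|---|---|---|---|---|---|
| 20 vs 10 | 0.25 | 19% | 11% | 17% | 2% |
| | 0.50 | 56% | 29% | 40% | 17% |
| | 0.75 | 89% | 56% | 39% | 50% |
| | 1.00 | 99% | 80% | 19% | 79% |
| 18 vs 9 | 0.25 | 17% | 10% | 15% | 2% |
| | 0.50 | 52% | 26% | 38% | 14% |
| | 0.75 | 85% | 51% | 42% | 43% |
| | 1.00 | 98% | 75% | 25% | 73% |

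With d = 0 each within-arm interval excludes zero in 5%. The between-arm interval excludes zero in 5% whatever d is, because a shared change cancels. A simulation of 200,000 trials at 18 vs 9 with d = 0.6 gave 5.0% for the between-arm interval and 43% for only GLPG1690 excluding zero, in line with the noncentral t.

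**What a between-arm QTcF interval would deliver.** For an assumed SD of change of 10, 15 or 20 ms, the half-width is 7.9, 11.9 or 15.9 ms at 20 vs 10, and 8.4, 12.6 or 16.8 ms at 18 vs 9.

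**The case against.** The strongest reply is that this is a small exploratory study whose safety analysis is openly descriptive. The SAP attaches no p-value and no decision rule to an interval that excludes zero, so the percentages above assume a way of reading that the SAP does not prescribe. That is correct, and it limits the point to how the tables are likely to be read.

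Several stronger readings are tempting and are not supported:

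- A reader might infer that the plan tests change from baseline. It does not: the intervals are labelled descriptive and formal testing is ruled out.
- A reader might infer that any change common to both arms will look like a drug effect. Both arms are in the same tables. At 1 SD both intervals exclude zero in 73% to 79% of cases, so the shared change is then visible.
- A reader might infer that the placebo arm goes unused. Shift tables and treatment-emergent abnormality frequencies are given by arm for all three domains. QT and QTcF are also categorised by absolute value and by change (SAP 5.4.4.3), and liver thresholds are counted (SAP 5.4.3.8).
- A reader might suspect that moving from triplicate to single ECGs at Weeks 16 and 24 creates a shared mean shift. Averaging replicates affects variance, not the expected mean.

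Two further replies carry some weight. The secondary endpoint is framed as adverse-event incidence and tolerability rather than mean QTcF or laboratory change, so the link to the objective is real but indirect. And SAP 3.5.2 requires n, mean, SE and SD, from which a reader can compute a two-sample t interval. The omission is therefore one of display. A baseline-adjusted difference, however, cannot be rebuilt from those summaries, and the by-arm categorical tables do not bound a difference in means.

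**Conclusion.** The point holds as a mismatch between the interval printed and the comparison the objective asks for. In the readable SAP, the only intervals for ECG, laboratory and vital-sign changes are within-arm (plus a pooled one for vital signs).

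The practical risk lies in moderate shared changes. Reading the two intervals separately, with no drug effect, only the GLPG1690 interval excludes zero in about 15% to 42% of cases for shared changes of 0.25 to 0.75 SD, per parameter and visit, against 5% for a between-arm interval. This rests on normal changes, equal SDs, the planned arm sizes with or without 10% dropout, and an assumed size of shared change. If placebo does not change, the problem disappears.

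No primary result is affected. This is an inexpensive improvement in presentation, with most value for QTcF.

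**What to change.** In SAP 5.4.3.9, 5.4.4.4 and 5.4.5.5, keep the by-arm summaries. At each analysis visit add the GLPG1690-minus-placebo difference in mean change from baseline with a two-sided 95% CI, from ANCOVA with the baseline value as covariate or from a two-sample t. Do this at least for QTcF, heart rate, AST, ALT, bilirubin and total serum bile acids. Label the intervals descriptive and unadjusted for multiplicity, and give no p-values, so that the rule against formal testing stands. State that any sentence about mean change relative to placebo will rest on this interval rather than on whether each arm's own interval covers zero.

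The cost is SAP wording and one line per parameter and visit in existing tables, with no new data. The downside is many wide intervals, with a half-width of about 0.8 SD. They will show imprecision and cannot exclude a modest QTcF effect, and the text should say so.

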#### 5.4.5. Vital Signs

##### 5.4.5.1. Available Data

The following vital signs parameters will be analyzed: Systolic Blood Pressure (SBP) (mmHg), Diastolic Blood Pressure (DBP) (mmHg), heart rate (bpm), respiratory rate (breaths/minute), and body temperature (°C). Vital signs will be analyzed regardless of assessment position. If there are more values available for a subject taken by different positions for a visit, then selection rules for the analyses will be applied as described in [Section 3.3.4](#). No adjustment to the temperature will be made to account for the possible different method of collection.

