## 6.3. INITIAL SUBJECT AND DISEASE CHARACTERISTICS

Subjects will be asked to attend the clinical study center for a screening assessment. After giving written informed consent, demographic data (age, sex, and race), and a medical history will be taken, including questions regarding medication intake. A physical examination will be performed, including measurement of weight and height.

Vital signs (systolic and diastolic blood pressure [SBP and DBP], heart rate, tympanic body temperature, and respiratory rate) will be measured and a 12-lead triplicate ECG will be recorded. Subjects should rest for at least 5 minutes in the supine position before the ECG recording, blood pressure, and heart rate measurement.

The inclusion and exclusion criteria will be checked to assess eligibility for the study. All screening tests will be reviewed to confirm eligibility before randomization and IMP intake.

Retesting of individual screening assessment(s) that did not meet eligibility criteria is not permitted, with the following exceptions AND only in case it is still possible to randomize the subject within the per-protocol defined screening period of 28 days:

- Laboratory values for LFTs, eGFR, and hemoglobin can be retested once.
- Lost or invalid blood or urine samples.

Rescreening: in case of screening failure, subjects are allowed to be rescreened maximum two times, after signing a new ICF. Rescreening can start at least 6 weeks after the initial laboratory testing of the previous screening.

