### 6.6.4. Vital Signs

Vital signs (SBP, DBP, heart rate, respiratory rate, and body temperature) will be recorded in a standardized manner (i.e. after the subject has rested in a supine position for 5 minutes) at visits specified in the Schedule of Activities in Section 6.11. Clinically significant abnormal values should be recorded as AEs.

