### **Selection of Visits**

Per parameter, analysis visit and timepoint, the value closest to the target date will be used in analysis tables and figures. Other values will be listed only. If more than one value is located at the same distance from the target day, then the latest in time will be selected. If there are two values on the same day and no time indicating which one is last, the average of the two will be calculated.

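### The SAP gives no preference to the supine vital signs that the protocol standardises, so if non-supine readings exist, a by-visit value or change from baseline can mix positions

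*SAP*

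**What the plan says.** Protocol 6.6.4 asks for vital signs "after the subject has rested in a supine position for 5 minutes". Protocol 6.3 asks the same for blood pressure and heart rate at screening: "Subjects should rest for at least 5 minutes in the supine position before the ECG recording, blood pressure, and heart rate measurement".

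SAP 5.4.5.1 sets position aside: "Vital signs will be analyzed regardless of assessment position". It then covers the case of several positions ("If there are more values available for a subject taken by different positions for a visit") by referring to the selection rules in SAP 3.3.4. Those rules have three steps:

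1. Per parameter, analysis visit and timepoint, "the value closest to the target date will be used in analysis tables and figures".
2. For ties, "If more than one value is located at the same distance from the target day, then the latest in time will be selected".
3. Two values on the same day with no time to order them are averaged.

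None of the steps mentions position. SAP 3.3.4 also brings unscheduled readings into the analysis windows.

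The abnormality outputs follow another route. SAP 5.4.5.4 takes the worst case over all post-baseline records, including unscheduled and follow-up visits. SAP 5.4.5.3 calls an L or H class treatment-emergent when it differs from the baseline class. Neither carries a condition on position.

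Position returns in one output only. The mean plots in SAP 5.4.5.5 are to be shown "with heart rate, respiratory rate, and blood pressure by position on a new page". SAP 5.1, which lists changes to the planned analyses, does not mention vital-sign position.

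**The concern.** The protocol fixes a posture so that readings are comparable between visits. The SAP foresees readings in other postures and lets them compete with the supine one on date and time alone. A change from baseline can then contain a posture difference as well as any change in the subject.

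The SAP also treats position inconsistently: it ignores position in the tables and splits by it in the plots. The plots show that the variable is expected in the data, so a preference for supine could be programmed.

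Safety and tolerability is the study's secondary objective. The arms are small enough for a single odd reading to show in a summary table.

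**Working it through.** The plan gives no figure to reproduce here. The check traces the written rules and then uses a small illustration.

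**Inputs from the documents.** Normal heart rate is 50 to 100 bpm (SAP Table 7). The Week 16 target is Day 113, and its analysis window is Days 86 to 141 (SAP Table 2). Planned arms are 20 and 10 (Protocol 7.1).

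**Assumptions.** The documents give no posture effect. I take a supine heart rate of 92 bpm, a normal supine baseline, and non-supine shifts of +5 to +20 bpm. These values only show how the rule behaves; they do not estimate an effect.

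**Step 1: two positions on one day.** Distance from target is tied, so clock time decides, or the values are averaged if times are missing. The supine reading comes first and the non-supine reading later.

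| Assumed shift | Selected if timed (92 + shift) | Average if untimed (92 + shift/2) | Worst case over all records above 100? |
|---|---|---|---|
| +5 | 97 | 94.5 | No |
| +10 | 102 | 97 | Yes |
| +15 | 107 | 99.5 | Yes |
| +20 | 112 | 102 | Yes |

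With times recorded, the by-visit value is the non-supine reading. Without times, it is a blend of two positions. The worst-case column does not depend on which value was selected.

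**Step 2: readings on different days.** Take a scheduled supine reading of 92 on Day 116 and an unscheduled sitting reading of 104 on Day 113. Distances from target are 3 and 0 days, so the rule selects 104 and only lists the supine value.

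**Step 3: effect on an arm mean.** One affected subject shifts the mean change by (shift ÷ n). For shifts of 5 to 15 units:
- n = 20: 5/20 = 0.25 to 15/20 = 0.75
- n = 10: 5/10 = 0.5 to 15/10 = 1.5

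**Step 4: effect on an arm's abnormality rate.** One subject more or fewer is 1/20 = 5 percentage points or 1/10 = 10 percentage points. This assumes that every subject has post-baseline data, since SAP 3.5.3 uses such subjects as the denominator.

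**Step 5: tables against plots.** SAP 3.3.4 selects one value per visit for tables and figures alike, while SAP 5.4.5.5 splits the plots by position. The SAP does not say whether selection comes before or after the split. If before, each position's plot holds only the subjects whose selected value was in that position. If after, the plots contain readings that the table did not use. Either way, plotted and tabulated means can differ once non-supine readings enter. If every reading is supine, they agree.

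**The case against.** The strongest reply is that no exposure is shown. The protocol requires supine readings, the visible text schedules no sitting or standing measurement, and the SAP sentence on several positions is conditional. If sites follow the protocol, the rule changes nothing. This stands, and it is why the point is minor.

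There are also safeguards. Clinically significant abnormal vital signs are recorded as adverse events (Protocol 6.6.4), values not selected are still listed, the analysis is descriptive without formal testing, and the by-position plots would help to reveal a posture effect. The primary endpoint is untouched. All of this stands, but none of it makes a by-visit change compare like with like.

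A reader might go further in three ways that the documents do not support:

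- **That the SAP chooses among positions by clock time.** Distance from the target day comes first. Time only breaks ties, and averaging needs same-day values without times.
- **That posture will be reported as a treatment-emergent abnormality, at a rate one can calculate.** Any such rate needs means, standard deviations and posture shifts that the documents do not give. A probability for an averaged value would not apply to the worst-case tables in any case, because those use every record.
- **That the worst-case tables should be limited to supine readings.** A low non-supine blood pressure at a visit with a normal supine reading would then leave the abnormality table and appear only in a listing. Using all records for the worst case is the SAP's safety convention for laboratory tests, ECG and vital signs alike, and there is good reason to keep it.

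**Conclusion.** The point holds as a minor gap between protocol and SAP. The protocol defines a supine measurement, and the SAP's selection rule does not prefer it. Where non-supine readings exist, by-visit values and changes from baseline can mix positions, and tables can disagree with plots.

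The overall size cannot be computed, because neither the number of non-supine readings nor the posture effect is in the documents. The per-subject effects in the working show only how sensitive the tables are. They rest on the planned arm sizes and, for the means, on assumed shifts. Nothing in the documents shows that non-supine readings will be common or unbalanced between the arms.

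**What to change.** Amend SAP 5.4.5.1 and align 5.4.5.5:

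- For baseline, by-visit summaries and change from baseline, select the supine reading when the analysis window holds one, and apply 3.3.4 only among supine readings.
- Use a reading in another position only when the window has no supine reading, and flag it.
- Draw the mean plots from the same selected data as the tables.
- Keep all records in the worst-case and treatment-emergent tables, but flag or footnote any abnormality that rests only on a non-supine reading against a supine baseline.

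The cost is a short wording change, a filter on a position variable that the plots already require, and a few flagged values. A supine reading further from the target day will sometimes replace a closer non-supine one. No record leaves the abnormality tables, and the unselected values remain in the listings.
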